2. EXTERNAL IRB REVIEW HISTORY*

NA

3. PRIOR APPROVALS:

NA

4. OBJECTIVES*

The main purpose of our study is to develop Tele-Navigation of Lung Cancer Screening (Tele-Navi LCS) – an intervention that is designed to improve patient awareness about the importance of LCS follow-up and to promote patient-provider communication about low-dose CT (LDCT) results, with the ultimate goal of increasing adherence to LCS. Our study has two specific aims:

Aim 1: Develop Tele-Navi LCS, using a co-production approach with patients at UMMH, and refine Tele-Navi LCS based on feedback from LCS stakeholders at UMMH, Wake Forest, UCHealth, and UPenn.

Aim 2: Pilot test Tele-Navi LCS and evaluate its feasibility, acceptability, and associated costs by implementing it in the clinical LCS workflow in primary care clinics at UMMH.

Because the data collected in Aim 1 may influence the activities of Aim 2, we will develop the majority of Aim 2 study materials at a later time. Aim 2 recruitment activities will not commence until these materials have been submitted to the IRB for review and approval.

5. BACKGROUND*

Adherence to follow-up after lung cancer screening (LCS) is essential to achieving mortality reduction and optimizing cost-effectiveness.¹⁻⁴ Large clinical trials, with adherence close to 100%, demonstrated that annual LCS with low-dose CT (LDCT) achieved approximately a 20% reduction in lung cancer death.^{5,6} These benefits resulted from timely detection, evaluation, and treatment of early stage lung cancer. Therefore, adherence to recommended follow-up is critical to improve survival in LCS.

Yet, even prior to the COVID-19 pandemic, adherence to follow-up in LCS was suboptimal. Adherence rates in community-based programs were between 16-59% compared to more than 80% in comprehensive LCS programs with greater resources and infrastructure.⁷⁻¹² In interviews with patients who had been screened at UMass Memorial Health (UMMH) (conducted as part of my K12 project), I found that: (1) many patients were not aware that LCS required at least annual follow-up, and (2) patients desired more communication with their providers about the results of their LDCT, including a clear follow-up plan. Interventions to improve patient awareness about the importance of LCS follow-up and to promote patient-provider

INVESTIGATOR STUDY PLAN - REQUIRED

communication about LDCT results are needed to improve adherence to LCS follow-up and achieve the full benefits of LCS.

The COVID-19 pandemic has been a major disruption to LCS, with routine LDCT postponed in order to minimize the risk of COVID-19 transmission.¹³ Since the LCS population is at high risk for developing severe COVID-19 infection due to their smoking history and comorbid illnesses, these patients may be even more likely to avoid regular health care, including LCS follow-up from fear of COVID-19.^{14,15} With expanded insurance coverage for telehealth during the present pandemic, many providers have started offering telehealth visits.^{16,17} The LCS population is, however, older and may have less access to or familiarity with telehealth, and may not be able to utilize telehealth to maintain their preventive and medical care without support.^{18,19} This digital divide may negatively affect their health outcomes. Our proposed intervention of providing patient navigation through telehealth will help to improve adherence to follow up among those undergoing LCS. In addition, by promoting and supporting the use of telehealth, this intervention may also help to reduce the “digital divide” in the LCS population.

Based on the well-established concepts of patient navigation that have been shown to promote cancer screening and its follow-up, and increased availability of telehealth, I propose to develop Tele-Navigation of Lung Cancer Screening (Tele-Navi LCS) using a patient portal and video-call with a navigator to improve adherence to LCS follow-up.²⁰⁻²⁵ I will co-produce intervention components of Tele-Navi LCS with patients who have undergone LCS at UMMH over the last three years. I will obtain feedback from various stakeholders including LCS physician champions, navigators, primary care providers (PCPs) and IT leadership at UMMH, designing Tele-Navi LCS to be scalable. Tele-Navi LCS will provide: 1) telehealth coaching for patients undergoing LCS to access a patient portal and a video-call, 2) a video-call from a Tele-Navigator prior to the next follow-up LDCT to a) improve patient knowledge about the importance of LCS follow-up, b) identify barriers to follow-up, and c) encourage patients to ask their PCPs about the results of LDCT, 3) subsequent secured portal messages to provide continuous support to patients, and 4) communication guide to support providers in discussing LDCT results with their patients.

6. INCLUSION AND EXCLUSION CRITERIA*

Patient Participants

Inclusion Criteria:

- Is eligible for LDCT for LCS follow-up
- Has technology to complete study activities (e.g., video call visit)
- English speaker

Aim 1 Additional Inclusion Criteria:

- Has UMMH PCP
- Has undergone LCS at UMMH in the past three years

Aim 2 Additional Inclusion Criteria:

- Has undergone LCS at UMMH
- Is overdue for LDCT follow-up

INVESTIGATOR STUDY PLAN - REQUIRED

Exclusion Criteria:

- Has previous diagnosis of lung cancer
- Has active cancer diagnosis
- Is a nursing home or group care resident
- Is pregnant

Stakeholder/Provider Participants

Inclusion Criteria Aim 1:

- Age ≥ 18
- Primary care provider/IT leader/lung cancer screening program leader/lung cancer screening navigator
- Works at UMass Memorial Health, Wake Forest Baptist Health, UCHealth, or UPenn

Inclusion Criteria Aim 2:

- Age ≥ 18
- Primary care provider
- Works at UMass Memorial Health

Vulnerable Populations

The following populations **will not be included** in this study:

- Individuals who are not yet adults (infants, children, teenagers)
- Pregnant women
- Adults unable to consent
- Prisoners

Since this is a small-scale study (~65 total subjects in 4 groups, with 3 different interviews and one intervention) it is not possible to have the study materials translated into other languages. If this pilot study shows promise, larger follow-up studies may focus on translating the intervention into additional languages.

7. STUDY-WIDE NUMBER OF SUBJECTS*

NA

8. STUDY-WIDE RECRUITMENT METHODS*

NA

9. STUDY TIMELINES*

Aim 1: Patient participants will begin by completing a baseline survey which will take ~30 minutes or less. Stakeholder participants will complete a brief (~5-10 minutes) online demographics survey (study factsheet will be included in the REDCap survey). Both patient and stakeholder participation will involve completing a one-time interview session held by telephone or by webinar (**Please note: we will follow all COVID-19 related guidelines and precautions, favoring remote activity whenever possible**). Interviews are expected to last approximately

INVESTIGATOR STUDY PLAN - REQUIRED

60-90 minutes for patients and about 30 minutes for stakeholders. Participation will be considered complete following the conclusion of the interview. Medical record review will occur to assess annual LCS follow-up; record review may occur over several follow-up years (up to 4 years).

Aim 2: Patient participation will involve completing a baseline survey which will take ~30 minutes or less. Following the baseline survey, the intervention will include a telehealth support call (or multiple calls) (~20 minutes) if the participant feels it would be helpful (to practice using a video call or accessing their patient portal), and at least one video call with a tele-navigator (educational outreach call) (~10 minutes). Finally, participants will be asked to complete a follow-up survey (~20 minutes). Participation is expected to take place over approximately 3-6 months. Medical record review will occur to assess annual LCS follow-up; record review may occur over several follow-up years (up to 4 years).

A sub-set of patient participants and providers of patient-participants will be recruited to engage in a one-time in-depth interview which is expected to last approximately 60 minutes.

Study Timeline*: Work Plan and Deliverables

Quarterly Milestones									
Aim	Quarters	1	2	3	4	5	6	7	8
1	Material Development	X							
	Co-production		X	X					
	Stakeholder interview		X	X					
2	Recruitment				X	X	X		
	Data collection				X	X	X	X	
	Data analysis			X				X	X
	Manuscript							X	X
Grant Preparation								X	X

***Note:** We plan to conduct longer-term collection of clinical follow-up data and additional data analysis for ~2 additional years.

10. STUDY ENDPOINTS*

Primary outcomes are adherence to follow up LDCT and feasibility of Tele-Navi LCS. Adherence is defined as LDCT completion at 3, 6 and 12 months from the due date (as in previous studies; this definition may change depending on the status of COVID pandemic) and will be measured by EHR data.^{7,8,10-12} For feasibility, we will assess how engaged patients are during telehealth coaching, video-calls by tele-navigator, telehealth visit and patient portal use. We will assess intervention fidelity by recording and comparing all telehealth coaching and video-calls by a tele-navigator against a pre-defined checklist of key elements.

Secondary outcomes are occurrence of patient-provider communication after LDCT; communication modality used; contents of the communication assessed by EHR review and a patient survey; patient understanding of the result of LDCT and follow-up plan assessed by patient surveys; and perception and acceptability of the intervention from patient surveys and

INVESTIGATOR STUDY PLAN - REQUIRED

interviews and provider interviews. We will also measure cost by tracking time required for training for a Tele-Navigator, all the intervention components provided by the Tele-Navigator, and time and any other resources required to implement Tele-Navi LCS into clinical workflow.

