24. LOCAL RECRUITMENT METHODS

All recruitment materials will be submitted to the IRB for review and approval prior to use in the study. While we will not accept referrals for the study, for communication purposes with clinical providers we will share/post a study flyer with various clinical groups within UMass Memorial Health (from which we will be recruiting patients). This flyer is intended to provide clinicians notification that the study is active and to provide contact information in case clinicians have questions about the study; it will not be patient-facing.

Patients: We will use a variety of methods to identify and recruit a diverse group of patient participants. Working with the informatics group at UMMH/UMass Chan we will search the UMMH patient database to identify eligible patients. Eligible patients will be sent an invitation to participate. The invitation will make clear that participation is voluntary, and will include contact information for expressing interest, or declining participation. We will follow-up about one week later by telephone with invitees who do not respond. We will make up to 10 phone call attempts (over a period of two to three weeks, varying the time of day and day of week phone attempts are made) and leave no more than 3 total voicemail messages. Research staff will confirm eligibility prior to enrolling subjects. We have successfully recruited and completed comparable interviews and research activities with patients in previous studies utilizing similar recruitment methods.

Stakeholders/Providers: We will recruit stakeholders/providers to complete a one-time interview.

Aim 1: Potential stakeholder participants (for example PCPs, LCS navigators, LCS program leaders, and IT leaders from UMMH, Wake Forest, UCHealth, and UPenn) will be identified by the Principal Investigator, leadership at LCS programs, leadership within the Implementation Science Center for Cancer Control at Wake Forest UCHealth, and UPenn (which have already provided letters of support), and stakeholder participants in Aim 1 using snowball sampling.

Aim 2: Potential UMMH provider participants (providers of patient participants in the intervention group) will be recruited as study participants.

INVESTIGATOR STUDY PLAN - REQUIRED

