25. LOCAL NUMBER OF SUBJECTS

Aim 1: We will recruit up to 50 participants for Aim 1. We aim to recruit a diverse sample of stakeholders including: patients (~6-12), PCPs (n~8), LCS navigators (n~7), LCS program leaders (n~8), Population Health leaders (n~6) and IT leaders (n~5).

Aim 2: Up to ~12 Aim 1 participants will be recruited to pilot test the intervention (but not enrolled in the Aim 2 intervention study). ~20 patients will be recruited to participate in the intervention. A smaller subset of ~5 intervention patients and ~5 providers whose patient participated in the study will be interviewed for in-depth feedback. Approximately 25 participants will be enrolled for Aim 2.

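### Primary adherence is timed from the LDCT due date, but Aim 2 enrols only overdue patients, so every window is shortened, and some can close, before enrolment

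*Combined protocol and SAP*

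**What the plan says.** Section 10 (Study Endpoints) states: "Primary outcomes are adherence to follow up LDCT and feasibility of Tele-Navi LCS". It then gives the time origin: "Adherence is defined as LDCT completion at 3, 6 and 12 months from the due date", taken from previous studies and measured from the electronic health record. The only flexibility it allows is that "this definition may change depending on the status of COVID pandemic".

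Section 6 lists, among the additional Aim 2 inclusion criteria for patients: "Is overdue for LDCT follow-up". It does not define overdue or set a maximum. The three-year limit on the last screen appears only under Aim 1.

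Section 24 describes patient recruitment by invitation: "We will follow-up about one week later by telephone with invitees who do not respond". Calls may then continue "over a period of two to three weeks". Section 25 puts the intervention group at about "20 patients will be recruited to participate in the intervention".

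Section 13 plans summary statistics and treatment cascades, with no sample size calculation. The note to the Section 9 work plan adds: "We plan to conduct longer-term collection of clinical follow-up data and additional data analysis for ~2 additional years".

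**The concern.** The endpoint and the entry criterion use different time origins. A due-date clock suits a programme that follows everyone from the date a scan falls due. Aim 2 instead takes people who have already missed that date, so part of each window has been used up before the navigator can act. No enrolled patient can have a completed scan in that elapsed part, since a patient who had been scanned would no longer be overdue.

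Two things follow. A patient whose window has already closed is a certain failure, unrelated to the intervention. The remaining patients have windows of unequal length, set by how overdue they were. The adherence figure then mixes response to navigation with overdue time at entry. Section 13 says the pilot is to inform a future study, including its outcome measures, so a figure pulled down in this way could mislead the next design. In a treatment cascade, a closed window would also look like a gap in patient flow.

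**Working it through.** The plan gives no numerical derivation for this endpoint, so there is no figure to reproduce. The check is window arithmetic.

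**Inputs from the documents.** Windows w = 3, 6 and 12 months from the due date (Section 10); overdue time d > 0 for every patient, with no cap (Section 6); about 20 patients (Section 25); up to 1 + 3 = 4 weeks, or about 0.92 month, from invitation to contact for non-responders (Section 24).

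**Assumptions.** The due date is the missed date. Overdue time is uniform on 0 to M months, with M = 3, 6, 12 or 24. After enrolment, scans are completed at a constant rate r per month, with r = 0.05, 0.10 or 0.20. The documents give neither the overdue distribution nor the rate.

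**Step 1: time left at enrolment** = max(0, w − d).

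| Months overdue | 3-month window | 6-month window | 12-month window |
|---|---|---|---|
| 1 | 2 | 5 | 11 |
| 3 | 0 | 3 | 9 |
| 6 | 0 | 0 | 6 |
| 12 or more | 0 | 0 | 0 |

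This step needs no assumption beyond the reading of the due date.

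**Step 2: expected number of 20 patients with the window already closed** = 20 × min(1, max(0, 1 − (w − L)/M)), where L is the contact lag. The second column of results gives every patient the full 4-week lag, so it is an upper bound: the calls apply only to non-responders.

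| Overdue range (months) | Closed at 3/6/12, no lag | Closed at 3/6/12, 4-week lag for all |
|---|---|---|
| 0–3 | 0 / 0 / 0 | 6.1 / 0 / 0 |
| 0–6 | 10 / 0 / 0 | 13.1 / 3.1 / 0 |
| 0–12 | 15 / 10 / 0 | 16.5 / 11.5 / 1.5 |
| 0–24 | 17.5 / 15 / 10 | 18.3 / 15.8 / 10.8 |

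Example: 0–6 months overdue, 3-month window, no lag: 20 × (1 − 3/6) = 10.

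**Step 3: the same behaviour counted on two clocks, no lag.** From enrolment, completion is 1 − exp(−r·w). From the due date, it is the average of 1 − exp(−r·max(0, w − u)) over u from 0 to M. With r = 0.10:

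| Clock | 3 months | 6 months | 12 months |
|---|---|---|---|
| From enrolment | 26% | 45% | 70% |
| Due date, 0–3 months overdue | 14% | 36% | 65% |
| Due date, 0–6 | 7% | 25% | 59% |
| Due date, 0–12 | 3% | 12% | 42% |
| Due date, 0–24 | 2% | 6% | 21% |

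Example: 12-month window, 0–24 months overdue: (12 − 0.699/0.10)/24 = 0.209.

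**Step 4: sensitivity of the 12-month figure to r.**

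| Overdue range (months) | r = 0.05 | r = 0.10 | r = 0.20 | Relative understatement |
|---|---|---|---|---|
| 0–3 | 0.408 vs 0.451 | 0.649 vs 0.699 | 0.876 vs 0.909 | 4–10% |
| 0–24 | 0.124 vs 0.451 | 0.209 vs 0.699 | 0.311 vs 0.909 | 66–73% |

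Each cell gives due-date versus enrolment completion. A range reaching 24 months is not extreme: with annual screening, even a three-year limit on the last screen, which Aim 2 does not have, would allow about 36 − 12 = 24 months overdue.

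**The case against.** The strongest objection is that the due date is undefined. Section 5 places the navigator's call ahead of the next follow-up scan, and Section 9 says record review will assess annual follow-up, so a later due date could be meant. That reading is possible but stated nowhere, and it is less natural for an overdue patient. A primary endpoint open to two readings needs clarifying in any case.

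Second, timeliness against the screening schedule is a legitimate quantity, and calling the result biased presumes that completion after enrolment is the target. That is fair as far as it goes: the understatement here is relative to completion after enrolment. But a measure that some patients must fail at entry cannot show what navigation achieved. Comparison with the earlier studies is weak too, because an overdue-only sample leaves out everyone who was scanned on time.

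Third, the stakes are modest. Section 4 frames Aim 2 around feasibility, acceptability and cost; there is no comparator or test; and the scan dates can be re-counted. This stands, and it limits the severity. Adherence is nevertheless named as a primary outcome.

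Fourth, the sizes rest on assumed distributions and run from trivial to large. That also stands. They show the range, not an estimate.

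**Conclusion.** The concern holds. On the natural reading of the due date, every Aim 2 window starts before enrolment, and the plan neither caps overdue time nor resets the clock. The shortening follows from Sections 6 and 10 alone. Whether windows are actually closed at entry, and how far the figure falls, depends on overdue time, which is not given. The effect at 12 months is small if patients are recently overdue and large if many are long overdue. The 3-month measure suffers most: under the 0.10 rate it drops from 26% to 14% even when nobody is more than 3 months overdue. This should be fixed, but it does not threaten the study: the consequence is a misleading primary figure in a descriptive pilot.

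**What to change.** In Section 10, define Aim 2 adherence as LDCT completion within 3, 6 and 12 months of enrolment (the consent or baseline survey date), with all enrolled patients as the denominator. Settle this before the first Aim 2 patient is enrolled, so that the clock is not chosen after results are seen. Record and report months overdue at enrolment. Keep the due-date version as a descriptive secondary measure and state which due date it uses.

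The cost is a wording change on the same record data. The drawback is that the primary measure departs from the definition borrowed from previous studies.

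On timing, recruitment ends with quarter 6 (month 18). The last 3-month result then falls at month 21, the last 6-month result at month 24 (end of quarter 8), and the last 12-month result at month 30. The work plan's data-collection row ends with quarter 7 (month 21), so the latest 6-month results and the 12-month results draw on the roughly two additional years of follow-up already planned, to about month 48.

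### Adherence is counted from the due date in patients enrolled already overdue, and scans booked before study contact or done before the navigator call are not separated from scans that follow the call

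*Combined protocol and SAP*

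**What the plan says.** Section 10 (Study Endpoints) states: "Primary outcomes are adherence to follow up LDCT and feasibility of Tele-Navi LCS". It continues: "Adherence is defined as LDCT completion at 3, 6 and 12 months from the due date", and says that this "will be measured by EHR data". It allows that the definition may change with the pandemic. It sets no rule on where the scan must fall relative to enrolment, telehealth support or the navigator call.

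Section 6 adds for Aim 2 patients: "Is overdue for LDCT follow-up". It sets no minimum or maximum lateness and does not mention a scan already ordered or booked.

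Section 5 (Background) lists, among the components of Tele-Navi LCS, "a video-call from a Tele-Navigator prior to the next follow-up LDCT". Telehealth coaching is another listed component.

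Section 9 gives the Aim 2 order: baseline survey, optional support call or calls, then "at least one video call with a tele-navigator (educational outreach call) (~10 minutes". Section 11 adds that educational materials are sent before the outreach session. No maximum interval from enrolment to that call is stated; participation lasts roughly 3 to 6 months. Before enrolment, Section 24 provides for an invitation and telephone follow-up: "We will make up to 10 phone call attempts (over a period of two to three weeks".

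Section 25 plans about 20 intervention patients. Section 24 mentions an intervention group, but no comparison group is described. Section 13 plans descriptive summaries and treatment cascades, reports no sample size calculation, and says that effectiveness will be studied along with process measures.

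**The concern.** The adherence clock starts before any patient can be enrolled, and the endpoint says nothing about what happened between that start and the scan. A patient who enrols overdue, has an appointment next week and is scanned before the navigator rings meets the definition. So does a patient who books and attends because of the call. Section 5 sets out the intended order of call and scan, but neither the endpoint in Section 10 nor the analysis in Section 13 carries it over.

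At stake is what the adherence figure can support. It is one of two primary outcomes, it comes from a single small group, and the pilot is meant to inform a later study, including its outcome measures. If the figure mixes scans that preceded the call with scans that followed it, readers cannot tell how much completion came after navigation. If the treatment cascade shows the call as a step before follow-up screening, some patients would appear to complete the last step before an earlier one.

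**Working it through.** The plan gives no target rate, sample size calculation or expected adherence, so there is no figure of its own to reproduce. I read completion at 3, 6 and 12 months as completion within those times.

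**Step 1. How each kind of scan is treated**

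| Scan | Counted as adherence? | Could the call have produced it? |
|---|---|---|
| Done before enrolment | Largely excluded: the patient is no longer overdue | No |
| Done between enrolment and the outreach call | Yes, if inside the window | No, though telehealth support may have come first |
| Booked before first study contact, attended after the call | Yes, if inside the window | Uncertain: the call may have helped attendance |
| Booked after first contact but before the call, attended after it | Yes, if inside the window | Uncertain, as above |
| Booked and attended after the call | Yes, if inside the window | Possibly |

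The last four rows are pooled.

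**Step 2. Weight of one scan.** With n = 20 (Section 25), one scan is 1/20 = 5 percentage points.

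**Step 3. How many scans could be affected.** The documents give no rate, so the share s of patients whose scan was booked before first contact or done before the call is assumed. The expected number is 20 × s, and the chance of at least one is 1 − (1 − s)^20.

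| Assumed s | Expected number | Chance of at least one |
|---|---|---|
| 5% | 1 | 64% |
| 10% | 2 | 88% |
| 20% | 4 | 99% |
| 30% | 6 | over 99% |

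For pre-call scans alone, assume a monthly return rate h with no intervention effect and a lag of g months from enrolment to call. The expected number is 20 × (1 − (1 − h)^g).

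| Assumed h | g = 1 month | g = 2 months |
|---|---|---|
| 2% | 0.4 | 0.8 |
| 5% | 1.0 | 2.0 |
| 10% | 2.0 | 3.8 |

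This range of 0.4 to 3.8 patients is 2 to 19 points, provided the window is still open when the scan is done.

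**Step 4. Illustration.** Suppose 8 of 20 are adherent: 40%, exact 95% interval 19% to 64%. If 1, 2 or 4 of the eight scans preceded the call, scans after the call number 7/20 = 35%, 6/20 = 30% or 4/20 = 20%. Dropping those patients from the denominator as well gives 7/19 = 37%, 6/18 = 33% or 4/16 = 25%.

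**Step 5. The opposite error.** For a patient L months overdue at enrolment, the part of window W left after enrolment is W − L. With L = 4 the 3-month window has closed (3 − 4 < 0). With L = 6 the 3- and 6-month windows have gone. With L of 12 or more, no window remains. Such patients count as non-adherent on those measures even if the call leads directly to a scan.

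**Step 6. Ordinary late return.** With no intervention effect, the expected adherent count is 20 × (1 − (1 − h)^(W − L)). Assuming every patient is 1 month overdue and h = 5%, this is 2.0, 4.5 and 8.6 of 20 at 3, 6 and 12 months. For h = 2% it is 0.8, 1.9 and 4.0; for h = 10% it is 3.8, 8.2 and 13.7. Most of this return can fall after the call, so no ordering of dates removes it.

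**The case against.** The strongest reply is that this is a feasibility pilot. Section 13 puts acceptability and process parameters first, and plans descriptive summaries with no test and no effect estimate. Scan dates come from the EHR and calls are run by the study, so pre-call scans could be identified later without touching the endpoint. This lowers the stakes but does not remove the point. Adherence is a named primary outcome, Section 13 speaks of effectiveness, and nothing commits the team to making the separation.

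A reader might also infer more than the documents support:

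- **That any scan after the due date counts.** It does not. The 3-, 6- and 12-month limits apply.
- **That scans during the recruitment calls inflate the figure.** Completed ones largely do not. Eligibility is confirmed before enrolment, and a patient already scanned is no longer overdue. Bookings made in that period are a different matter.
- **That the plan says pre-call or pre-booked scans will be counted.** It does not say so. This follows from the absence of any rule.
- **That a pre-call scan owes nothing to Tele-Navi LCS.** Sections 5, 9 and 11 make coaching part of the intervention, so such a scan may follow partial delivery.
- **That a scan booked earlier cannot follow from the call.** A patient who is called and then keeps an existing appointment received the call in the intended order.
- **That adherence is biased upward.** Closed windows pull the other way.

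**Conclusion.** The point holds in a limited form. As written, the primary adherence measure pools scans completed before the outreach call, scans booked earlier and attended after it, and scans that were both booked and attended after it. Each pre-call scan inside the window adds 5 points that the call cannot have produced; earlier-booked scans attended after the call are of uncertain attribution. The net direction of bias is unknown, because the due-date anchor also shuts out patients whose windows closed before enrolment.

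The 5-point weight rests on about 20 patients. The affected shares, monthly return rates and lags are assumptions. The community adherence range of 16–59% in Section 5 does not supply them, because it is not a rate for overdue patients. The point does not undermine the feasibility or acceptability aims. It is worth correcting because it is cheap and determines what the adherence figure can be used for.

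**What to change.** In Sections 10 and 13, specify that the following are taken from the EHR and study logs: due date, order and booking dates, scan date, and the dates of first study contact, enrolment, first telehealth support and outreach call.

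Keep total completion at 3, 6 and 12 months, described as observed completion and not as an intervention effect. Beside it, over the same denominator of enrolled patients, report four mutually exclusive groups:

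1. Scan completed before the outreach call, noting whether telehealth support had been given. A scan in a patient who never receives the call also goes here, marked as such.
2. Scan completed after the call but booked before first study contact.
3. Scan completed after the call and booked after first study contact but before the call.
4. Scan booked and completed after the call.

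Use the same ordering in the treatment cascade. Report months overdue at enrolment, so that readers can see how many patients could still meet each window. Moving the clock to enrolment would address closed windows, but it would not by itself separate pre-call scans. State that the split does not remove ordinary late return after the call, which needs a comparator or a background rate for overdue patients.

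The cost is a few date fields in an EHR pull already planned and some wording in two sections. The downside is small subgroup counts, so the figure for completion following navigation will be lower and less precise than the total.
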